9.9 Image Interpretation

CT and ultrasound images will be read at the site according to usual clinical practice to facilitate patient management decisions.

Images will also be read in a central independent blinded read in order to assess image quality/diagnostic confidence.

Images will be read by a panel of independent blinded readers appropriately qualified in abdominal imaging. Each CECT (CTA) image or NECT image plus duplex ultrasonography image will be read by 3 independent readers who will be randomly selected from the panel.

Detailed reader selection criteria will be provided in the Independent Read Charter. Readers will be provided with a Reader Training Manual for CECT and NECT plus Ultrasound assessments. This manual will provide the detailed assessment criteria which will include, but are not limited to, the diagnosis of the following items with regard to their confidence in making patient management decisions: i.e., status of the graft, stenosis, aneurysm rupture, endoleaks. A 5-point scale will be used to rate the visual assessment of image quality/diagnostic confidence:

5= excellent image quality, highest confidence for use in treatment decisions

4= good image quality, good confidence for use in treatment decisions

3= sufficient image quality, moderate confidence for use in treatment decisions

2= restricted image quality, low confidence for use in treatment decisions

1= poor image quality, no confidence for use in treatment decisions

A rating of 1 or 2 equates to the images being considered non-diagnostic. If a reader gives a 1 or 2 rating, the reader will be required to enter the reason for that rating in a freeform text entry field.

10 EFFICACY, SAFETY, AND OTHER VARIABLES

10.1 Endpoints

10.1.1 Primary Endpoint

Incidence of AKI stage ≥ 1 (AKIN SCr criteria) following an i.v. injection of iodinated iso-osmolar contrast material iodixanol (VisipaqueTM Injection 320 mgI/mL) or saline in patients with CKD stage III/IV assessed at 48 hours post-baseline (Follow-up 1).

10.1.2 Secondary Endpoints

AKI Secondary Endpoints:

- Incidence of AKI stage ≥ 2 (by AKIN SCr criteria) following an i.v. injection of iodinated iso-osmolar contrast material iodixanol (VisipaqueTM Injection 320 mgI/mL) or saline in patients with CKD stage III/IV assessed at 48 hours post-baseline (Follow-up 1).
- Incidence of AKI (by standard definition of CIN [[Mehran and Nikolsky 2006](#)]) following an i.v. injection of iodinated iso-osmolar contrast material iodixanol (VisipaqueTM Injection 320 mgI/mL) or saline in patients with CKD stage III/IV assessed at 48 hours post-baseline (Follow-up 1).
- Incidence of AKI stage ≥ 2 (by Waikar criteria [[Waikar and Bonventre 2009](#)]) following i.v. administration of iodinated iso-osmolar contrast material iodixanol (VisipaqueTM Injection 320 mgI/mL) or saline in patients with CKD stage III/IV assessed at 48 hours post-baseline (Follow-up 1).

Other Secondary Endpoints:

- Mortality and morbidity (i.e. critical events, including EVAR-related post-baseline events, as adjudicated by the CEAC) assessed at 6 months (Follow-up 3) in patients with CKD stage III/IV.
- Blinded independent assessment of image quality/diagnostic confidence using a 5-point scale.

10.1.3 Exploratory Endpoints

- [REDACTED]
- [REDACTED]
- [REDACTED]

10.2 Safety Assessments

The Investigator(s) and the Sponsor/CRO will review the safety data. The following safety data will be collected and evaluated:

- Clinical laboratory parameters: clinical chemistry, hematology, biomarkers and urinalysis ([Table 2](#)).
- Vital signs: systolic/diastolic blood pressure, respiration rate, heart rate.
- 12-lead ECG (screening only).
- Physical examination.
- AEs and SAEs.
- Pre-specified normal limits for vital signs are provided in Section [15.3](#).

10.2.1 Clinical Laboratory Evaluation

Clinical laboratory parameters assessed in this study are displayed in [Table 2](#). Local laboratories will be used for measuring screening parameters. A central laboratory will be used for analysis of SCr, cystatin C, and N-GAL biomarkers at Baseline, Follow-Up 1, Follow-Up 2 (if a clinic visit takes place), and Follow-Up 3 (SCr only).

Table 2 Clinical Laboratory Parameters

Screening	Baseline	Baseline 4 hours post scan	Follow-Up 1 (48 hours \pm 6 hours)	Follow-Up 2 (7 days \pm 2 days)	Follow-Up 3 (6 months \pm 2 weeks)

Local Laboratory:
 
Clinical Chemistry:
 
Chloride
 
Urea nitrogen
 
Serum creatinine
 
Bicarbonate
 
Sodium
 
Potassium
 
Glucose
 
Alkaline phosphatase
 
Aspartate transaminase
 
Alanine transaminase
 
Bilirubin (Total)
 
Thyroid-stimulating hormone (TSH)^a
 
Hematology:
 
Hematocrit
 
Hemoglobin
 
Platelet count
 
White blood cell (WBC) count
 
Lymphocyte %
 
Urinalysis (local lab):
 
Glucose
 
Ketone
 
Protein
 
Blood
 
Pregnancy Test:
 
Urine dipstick
	
Central Laboratory:
 
Clinical Chemistry:
 
Serum creatinine
 
Cystatin C
 
Neutrophil gelatinase-associated lipocalin (N-GAL)
 
Local Laboratory:
 
Urinalysis:
 
NephroCheck® biomarkers (TIMP-2, IGFBP-7)^b
 
Local Laboratory:
 
Urinalysis:
 
NephroCheck® biomarkers (TIMP-2, IGFBP-7)^b
 
Pregnancy Test:
 
Urine dipstick
	
Local Laboratory:
 
Urinalysis:
 
NephroCheck® biomarkers (TIMP-2, IGFBP-7)^b
	
Central Laboratory:
 
Clinical Chemistry:
 
Serum creatinine
 
Cystatin C
 
N-GAL
 
Local Laboratory:
 
Urinalysis:
 
NephroCheck® biomarkers (TIMP-2, IGFBP-7)^b
	
Central Laboratory:
 
Clinical Chemistry:
 
For patients having met the primary AKI criteria:
 
Serum creatinine
 
Cystatin C
 
N-GAL
	
Central Laboratory:
 
Clinical Chemistry:
 
Serum creatinine

a supersensitive TSH (sTSH) assay if locally available

b If local testing is available

The investigator will review laboratory test results to determine the occurrence of clinically important abnormalities which will be reported as AEs. The signed and interpreted laboratory results will be kept together with the patient's eCRF as supplemental pages, both centrally and at the site.

Blood samples will be obtained for assessment of clinical chemistry and hematology at the various pre- and post-treatment time points described in [Table 1](#). Samples will be analyzed at a central laboratory for all samples other than those obtained to confirm eligibility for enrollment (for parameters, see [Table 2](#)). All blood samples will be processed and handled per standard laboratory procedures. Any retained samples will be destroyed at completion of the study.

Urine will be collected at the various pre- and post-treatment time points described in [Table 1](#). Urine voided will be analyzed for the parameters listed in [Table 2](#).

Procedures for obtaining, preparing and shipping blood samples will be detailed in a laboratory manual provided to each study center.

Any abnormal laboratory findings that constitute an AE (e.g., any abnormal findings leading to an intervention other than repeating the laboratory test) should be reported as such and should be followed up until the outcome is known. Also, additional diagnostic tests may be indicated to determine a more precise diagnosis of the patient's condition (e.g., ordering a white blood cell (WBC) differential to help characterize a high or low WBC count, or ordering a determination of red cell indices to help characterize a low hematocrit).

10.2.2 Vital Signs

Before vital signs are measured, the patient should rest for at least 5 minutes (if possible). Vital signs (blood pressure, heart rate, respiratory rate) will be recorded in the sitting position at Screening, Baseline (prior to Visipaque™ or saline placebo administration), and within 1 hour post-administration, at Follow-Up 1 (48 hours post-administration), and at Follow-Up 2 (7 days post-administration; only for patients with AKI stage ≥ 1) according to the study schedule of events ([Table 1](#)). The same, i.e. sitting, position will be used each time vital signs are measured for a given patient and blood pressure will be measured from the arm contralateral to the site of Visipaque or saline placebo administration whenever possible.

10.2.3 ECG

A standard 12-lead ECG will be obtained at Screening or at the latest at Baseline ([Table 1](#)). All ECG recordings will be read at the investigational site prior to the patient being randomized.

Patient management decisions may be based on the 12-lead ECG findings.

10.2.4 Physical Examination

A qualified physician, (or other healthcare professional licensed to perform physical examinations), will conduct physical examinations. The physical examination will include recording an assessment for the presence of abnormalities of the following: general appearance, skin, head, eyes, ears, nose, throat, lungs, cardiovascular system, back and spine, abdomen, extremities, injection site, lymph nodes, and neurological exam.

In the event that *new* abnormal physical findings and *worsening* abnormal physical findings are encountered during the study, these terms are defined as follows: a new abnormal physical finding is defined as one that occurs when a patient's normal baseline physical examination becomes abnormal post baseline; a worsening abnormal physical finding is defined as one that occurs when a patient's abnormal baseline physical examination becomes worse post baseline.

10.2.5 Critical Study Events

Critical events include, but are not limited to:

- Death
- Major Adverse Renal Cardiac Event (MARCE)
- Renal replacement therapy (dialysis, hemofiltration/ultrafiltration, renal transplant)
- Hospitalization due to worsening renal impairment/renal failure
- EVAR-related post-baseline events

Critical events will be identified by the Investigator, documented in the CRF, and adjudicated according to the CEAC Charter.

A critical event is expected to be associated with a reported AE or SAE. More than one critical event may be associated with the same AE or SAE and the terms reported for critical events and AEs/SAEs can differ. Refer to Section 10.2.6 for further information.

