8.4 Blinding

This study is not blinded.

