9.7 Critical Events Adjudication Committee

The CEAC will adjudicate the study critical events (including EVAR-related post-baseline events, as defined and listed in the CEAC charter) in a blinded fashion. It will be comprised of qualified physicians who are experts in the field of nephrology, and other specialties as appropriate, who have relevant experience within clinical trials and are independent from the Sponsor and study centers. The CEAC will be composed of 4 members and governed by a specific CEAC Charter, approved by the CEAC members and the Sponsor. Three members will be required to adjudicate on each critical event and agree on an outcome following review of all available clinical information. The possible outcomes are as follows:

- (1) The event is a study endpoint and there is unanimous agreement on its classification: the event is validated;
- (2) There is unanimous agreement that the event is not a study endpoint;
- (3) More information is required: the CEAC will request more information from the study center via the process defined in the CEAC Charter;
- (4) The event could be a study endpoint, however there is a disagreement on its classification.

In the case that additional information is requested, a second review with the additional information received from the study center will aim to classify the event into the first or second outcome described above.

All cases that cannot be unanimously adjudicated, or where there is a disagreement, will be reviewed in common to obtain a final decision.

Whenever possible, adjudications will be completed remotely using electronic systems that comply with legal and regulatory requirements.

The CEAC decisions will be based on members' blinded reviews of the data provided by Investigators via a CRO. Data provided may include AE, SAE and critical event reports, eCRF downloads, hospital admission/discharge reports and any specific documents requested by a CEAC member. All information will be provided in an anonymized format.

The CEAC will be appointed at the commencement of the study before any patients have been enrolled.

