Other secondary endpoint analyses will be conducted using the safety population for stage III/IV combined. In addition, these summaries and analyses will be repeated for the stage III CKD subgroup and the stage IV CKD subgroup separately.

Mortality and morbidity events:

- All-cause death assessed at 6 months (Follow-up 3).
- Critical events (including EVAR-related post-baseline events as adjudicated by the CEAC) assessed at 6 months (Follow-up 3).
- Incidence rate of hospitalization due to renal failure assessed at 6 months (Follow-up 3).
- Incidence of requirement for renal replacement therapy (i.e., renal transplant, dialysis, or hemofiltration/ultrafiltration) assessed at 6 months (Follow-up 3).
- Incidence of the composite of death and hospitalization events due to renal failure assessed at 6 months (Follow-up 3).
- Hospital length of stay (LOS) in days assessed at 6 months (Follow-up 3).
- Incidence rate of patients with $\geq 30\%$ reduction in eGFR at 48 hours compared to baseline.
- Other criteria defined by the CEAC.

Among the morbidity and mortality events, binary variables will be analyzed using the noninferiority test for proportions described above. Hospital LOS will be summarized descriptively by arm.

[figure not shown]
Image quality/diagnostic confidence analyses:

- Image quality/diagnostic confidence will be rated on a scale of 1 to 5. The frequency distribution of image-quality/diagnostic confidence ratings will be summarized for each type of imaging procedure in each treatment arm. Thus, there will be 2 separate summaries of image quality/diagnostic confidence ratings, CECT and NECT plus non-contrast duplex ultrasonography images. Both by-reader and majority-read analyses will be performed for each summarization.
- The image-quality/diagnostic confidence ratings will be analyzed based on individual scores and will also be dichotomized as evaluable (rating of 3 to 5) or nonevaluable (rating of 1 or 2). The frequency distribution of evaluable vs nonevaluable image quality/diagnostic confidence ratings will be summarized for each treatment group. Thus, there will be 2 separate summaries of image quality/diagnostic confidence ratings: CECT and NECT plus non-contrast duplex ultrasonography. Both by-reader and majority-read analyses will be performed for each summarization.

No statistical comparisons between the CECT images and NECT images plus duplex ultrasonography images will be made.

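### No stated rule sends unflagged hospitalizations to the blinded events committee, so referral of six-month events that need a judgement of cause starts with an investigator who knows the arm

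*Combined protocol and SAP*

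**What the plan says.** Section 8.4 states that "This study is not blinded". Section 10.2.5 lists the critical events and gives the route into adjudication: "Critical events will be identified by the Investigator, documented in the CRF, and adjudicated according to the CEAC Charter". One listed category is "Hospitalization due to worsening renal impairment/renal failure", which applies only once a cause has been assigned to the admission. The list is described as not exhaustive.

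Section 9.7 takes over from there: "The CEAC will adjudicate the study critical events". Members decide from "blinded reviews of the data provided by Investigators via a CRO". On content, "Data provided may include AE, SAE and critical event reports, eCRF downloads, hospital admission/discharge reports" and any document a member asks for. On document handling, "All information will be provided in an anonymized format". The committee can unanimously decide that a referred event is not an endpoint. No section describes a route for finding an event that was never referred.

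Section 12.7.1 includes, among the mortality and morbidity endpoints, "Incidence rate of hospitalization due to renal failure assessed at 6 months (Follow-up 3"), and the composite of death and renal hospitalization. Binary endpoints in that group get the same noninferiority test for proportions as the primary endpoint, with a margin of 5 percentage points.

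**The concern.** Blinded adjudication protects an open-label trial only for the events that reach the committee. A hospitalization with mixed cardiac and renal features has to be called renal, or not, before it is a critical event. The first person to make that call knows the arm. An investigator who suspects contrast may flag such an admission more readily after iodixanol than after saline; one who believes contrast is harmless may do the reverse.

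The visit schedule does little to fill the gap. Under Sections 9.4 and 9.5, a patient without AKI at 48 hours has a telephone call at day 7 and nothing further scheduled until month 6. An admission in month 2 is known only through site reporting.

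If referral differs by arm, the difference enters before blinding, and the committee cannot restore what it was not sent. The adjudicated label would then suggest more protection than the process gives.

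**Working it through.** **1. The route to the committee, section by section**

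- 10.2.5: the investigator identifies critical events.
- 9.7: the committee adjudicates critical events. SAE reports and admission records may be among the data. The wording is permissive, the data come from investigators, and it reads as support for events already under review.
- 10.2.9: a footnote defining the follow-up period mentions SAEs alongside critical events in connection with adjudication. It does not say that every SAE is sent.
- 12.8: the overall AKI rate for the sample size re-estimation is the one determined by the committee, so some AKI data reach it. No trigger is given for hospitalizations.
- 10.2.6: an AE or SAE for AKI is mandatory when SCr rises by at least 0.3 mg/dL or to at least 1.5-fold, from baseline or from the previous result. This feeds the CRF; no link to the committee is stated.
- 10.2.7: hospitalizations associated with an AE are SAEs.

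The data for an objective trigger are therefore collected, but no section turns them into a referral rule.

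**2. The plan's own figure**

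Inputs from Section 12.8: 10% in both arms, margin 0.05, one-sided 0.025, power 80%, score test. The restricted estimates at the margin are 0.1303 and 0.0803.

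s0 = √(0.1303 × 0.8697 + 0.0803 × 0.9197) = 0.4326; s1 = √(2 × 0.10 × 0.90) = 0.4243

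n = [(1.960 × 0.4326 + 0.8416 × 0.4243) / 0.05]² ≈ 581 per arm

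The plan's 582 is reproduced; power at 582 is 80.1%. The sample size is not in dispute. The steps below use 582 per arm and the planned Miettinen-Nurminen method.

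**3. Low event rate, no true effect**

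The documents give no rate for renal hospitalization. Assume 3% in each arm, with 90% of events flagged in one arm and 60% in the other.

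- True events: 0.03 × 582 = 17.5 per arm.
- Seen by the committee: 17.5 × 0.90 = 15.7 and 17.5 × 0.60 = 10.5.
- Spurious difference: 5.2 / 582 = 0.9 points; ratio 0.90 / 0.60 = 1.5, or 0.67 if the arms are swapped.
- With milder flagging of 80% and 70%, the ratio is 0.80 / 0.70 = 1.14.

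95% intervals, contrast minus control:

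| Events seen (contrast vs control) | Interval, points |
|---|---|
| 17 vs 17 | −2.0 to +2.0 |
| 16 vs 10 | −0.7 to +2.9 |
| 10 vs 16 | −2.9 to +0.7 |

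All three upper limits are below 5. Noninferiority would fail only at about 32 vs 17 or 27 vs 10 events.

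**4. True excess harm exactly at the margin**

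Probability of concluding noninferiority wrongly, from 200,000 simulated trials per cell. The event rates and referral shares are assumptions.

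| True rates, contrast vs control | Full referral | 90%, contrast only | 80%, contrast only | 80%, both arms | 80%, control only |
|---|---|---|---|---|---|
| 6% vs 1% | 2% | 7% | 20% | 15% | 1% |
| 8% vs 3% | 2% | 8% | 23% | 12% | 1% |
| 10% vs 5% | 2% | 9% | 27% | 10% | under 1% |

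Under-referral in the contrast arm makes false noninferiority more likely. Under-referral in the control arm alone makes it less likely (0.4 to 1.4%). Equal under-referral in both arms also raises it, because a risk difference shrinks in proportion to the share of events captured.

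**The case against.** A reader might infer that the committee sees nothing except what the investigator calls critical. The documents do not support that. Section 9.7 allows SAE reports, eCRF downloads and admission records to reach it, the footnote in Section 10.2.9 can be read as including SAEs, and Section 12.8 has it determine AKI. What stands is narrower: none of these is a screening rule.

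A reader might also infer that a few unflagged events would change the noninferiority result. At low rates they would not, as step 3 shows. The ratio of 1.5 is not a planned statistic, and the larger error rates in step 4 arise only when true harm is placed at the margin.

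The mandatory AKI report in Section 10.2.6 is a fair counter. An admission for heart failure with a creatinine rise over the threshold would need an AKI report in either arm, so it should not be recorded only as a cardiac event. The missing piece is the link from that report to the committee.

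On masking, it would be wrong to say that the files need only be anonymized. Section 9.7 requires blinded review, and the synopsis says the committee will have no access to unblinded data. What is absent is a description of how arm-revealing text, such as a mention of contrast or of the duplex scan, is removed.

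Finally, critical events are defined in the Charter, which may contain both a referral trigger and a masking procedure. If so, a short cross-reference settles the point.

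**Conclusion.** The point holds as a gap in the stated referral rule, subject to the Charter. It concerns secondary six-month endpoints that need a causal label: renal hospitalization, its composite with death, MARCE and EVAR-related events. These lie outside the hierarchical testing of the AKI secondary endpoints. The primary endpoint rests on central-laboratory creatinine, and death and renal replacement therapy need little judgement to identify.

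The direction of any bias cannot be known in advance. At an assumed 3% per arm, even 90% against 60% flagging moves the estimate by 0.9 points and leaves the noninferiority conclusion unchanged. With true excess harm at the 5-point margin, 90% or 80% referral in the contrast arm alone raises false noninferiority from about 2% to about 7 to 9% or 20 to 27%. These sizes rest on assumed event rates and referral shares and on 582 patients per arm. The documents give no evidence that referral would in fact differ by arm. The change is worth making because it is cheap.

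**What to change.** In Sections 10.2.5 and 9.7, keep investigator-flagged events and add a listing that the CRO runs on the database, with the same rule in both arms. The listing refers to the committee:

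- every death;
- every renal replacement therapy;
- every hospitalization SAE with a renal or urinary MedDRA term, a concurrent AKI AE or SAE, or a reported SCr rise meeting the Section 10.2.6 threshold.

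This trigger serves the renal endpoints. For MARCE and EVAR-related events, the sponsor should confirm whether the Charter sets an equivalent one. If the Charter already contains the whole rule, cite it in Section 10.2.5.

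As a secondary wording point, Section 9.7 should say that files are masked for arm as well as anonymized, with references to contrast or saline, CECT or NECT, and the duplex scan removed. This carries out the blinded review already required.

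The cost is protocol and Charter wording, a database listing, somewhat more files for the existing committee, and redaction by the CRO. No patient procedure changes, and the listing uses events and results already reported. It cannot recover admissions or creatinine values that a site never reports.
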